**Logistic regression:**

A logistic regression model will be used to study the association between membership to each of the two extreme treatment response groups with each of the possible clinical factors of interest (see the study factors in point 7.1. Primary objective).

## 9.2 STATISTICAL ANALYSES

### Primary objective

A descriptive analysis will be performed of the baseline clinical characteristics (clinical history of renal cell carcinoma, first-line treatment, other treatments prior to axitinib) of the population of patients who are long-term responders with axitinib, in those patients refractories to treatment, and overall.

The baseline clinical characteristics will be statistically compared according to membership to each one of the two extreme treatment response groups.

Efficacy variables will be analyzed and compared between groups of long responders and refractory patients: PFS, time to progression, overall survival, overall survival from the beginning of the 1st line. These analyzes will be added in the statistical report in the sections in which these same analyzes are shown for the total N of patients.

In addition, the association of clinical factors of interest with the benefit of treatment will be analysed by logistic regression (see point 7.1. Primary objective).

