## **8. METHODS OF INVESTIGATION**

The purpose of this study is to describe, in routine clinical practice, outside the context of a clinical trial, the clinical characteristics of patients with metastatic kidney cancer who have been treated with axitinib for at least 9 months and to identify clinical factors associated with a greater benefit from the drug. No hypotheses have been pre-specified, and all study data will be analysed using the statistical descriptive techniques.

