**Inclusion criteria**

Patients must meet all the inclusion criteria below to be eligible for inclusion in the study:

1. IC1: Evidence of a personally signed and dated informed consent document indicating that the patient (or his/her legal representative) has been informed of all relevant aspects of the study. Informed consent will only be obtained from patients who are still alive.
2. IC2: Aged 18 or over.
3. IC3: Histologically confirmed diagnosis of advanced renal cell carcinoma, with at least one radiological evaluation of the disease according to RECIST 1.1 criteria.
4. IC4: Treatment with axitinib, as second-line or further line treatment and with progression-free survival PFS of 9 months or more or with disease progression at the first response assessment.

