**Cohort treatment/labelling**

For the study, “long-term responders to axitinib” have been defined as patients with a PFS for at least 9 months with the drug, and “refractory patients to axitinib” have been defined as patients with disease progression in the first assessment since the initiation of treatment (estimated PFS  $\leq 3$  months).

See point 5.2. *subgroups*, and in group 7 *Definition of variables and objectives*, how these groups are defined in terms of CRFs variables and algorithmic conditions of computer programming for the patient’s classification.

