#### **5.2 SUBGROUPS**

For some of the study objectives, the following two groups of patients with extreme responses to the drug are defined (see definition in point 7. Definition of variables):

- “Long-term responders to axitinib”: Patients who have a PFS of at least 9 months with the drug.
- “Patients primary refractory to axitinib”: Patients with disease progression at the first assessment after the initiation of treatment (estimated PFS  $\leq 3$  months). It means, patients with best response to axitinib=PD.

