 $(\text{Dose increase date or Dose reduction date} - \text{Start date of treatment with axitinib}) / 30.4375$
  - Duration (months) of subsequent treatments =  
 $(\text{Date of end of subsequent treatment or of latest follow-up if not suspended} - \text{Date of start of subsequent treatment}) / 30.4375$ . In the case of several subsequent treatments per patient, proceed as follows: the duration in months of each of the subsequent treatments will be calculated (from the start date to the end date or last check if it continues). This will be done for all subsequent treatments and then proceed to make the sum per patient of all durations of subsequent treatments

- Progression-Free Survival (PFS, in months) =  
 (Date of Disease Progression on treatment with axitinib or death from any cause – Date of start of treatment with axitinib) / 30.4375  
 If there is no progression or death, the case is censored as  
 PFS (months) = (Date of latest follow-up – Date of start of treatment with axitinib) / 30.4375
- Time to progression (TTP, in months) =  
 (Date of Disease Progression – Date of start of treatment with axitinib) / 30.4375  
 If there is no progression, the case is censored as  
 TTP (months) = (Date of latest follow-up – Date of start of treatment with axitinib) / 30.4375
- Overall Survival (OS, in months) = (Date of death – Date of start of treatment with axitinib) / 30.4375  
 If death has not occurred, the case is censored as  
 Overall Survival (OS, in months) = (Date of latest follow-up – Date of start of treatment with axitinib) / 30.4375
- Overall Survival since the start of first-line treatment (OS, in months) = (Date of death – Date of start of first-line treatment) / 30.4375  
 If death has not occurred, the case is censored as  
 Overall Survival (OS, in months) = (Date of latest follow-up – Start date of first treatment) / 30.4375
- Patient subgroups
  - A-Long-term responders: comprising patients with PFS  $\geq 9$  months.
  - B-Refractory (primary): comprising patients with best response to treatment = PD. This date is collected in the CRF form “axitinib treatment”.
- MSKCC risk group (described in appendix 11.1.). It will be analysed “Before the beginning of the first line”. These calculations will be performed on patients who have data on all the variables involved (in the case of a patient who does not have data on all the variables but has > 2 factors, it will be classified in the “Poor” risk group.

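### SAP 9.2 has PFS, TTP and OS compared between groups that are defined by PFS and best response; a test there would be circular for PFS and TTP and biased towards long responders for OS

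*SAP*

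**What the plan says.** **Groups.** SAP 5.2 defines long responders as "Patients who have a PFS of at least 9 months with the drug". SAP 7 defines the other group as "B-Refractory (primary): comprising patients with best response to treatment = PD". SAP 2.1 (cohort labelling) describes the refractory group as having "disease progression in the first assessment since the initiation of treatment", with an estimated PFS of at most 3 months. The rule in SAP 7 sets no upper limit on PFS.

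**Comparison.** SAP 9.2, under the primary objective, says: "Efficacy variables will be analyzed and compared between groups of long responders and refractory patients: PFS, time to progression, overall survival", and adds OS from the start of first line. These results are to appear "in the sections in which these same analyzes are shown for the total N of patients".

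**Tests.** SAP 9.1 assigns the log-rank test, two-sided at 0.05, when survival functions need to be compared. SAP 4 plans no multiplicity adjustment.

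**Text that points to description only.** Just before the efficacy sentence, SAP 9.2 says: "The baseline clinical characteristics will be statistically compared". The adverb is not repeated for efficacy. SAP 7.1 limits PFS within each group to a descriptive summary. SAP 9.2 makes all secondary objectives descriptive. Protocol section 8 says "all study data will be analysed using the statistical descriptive techniques".

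**Association list.** SAP 7.1 orders an association analysis of listed factors with group. The list includes best response to axitinib, whether the disease progressed, and axitinib duration. The logistic model that follows takes only factors that precede axitinib, screened by p-value.

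**The concern.** A comparison of two groups on the outcome that sorted patients into them says nothing about the patients; it restates the sorting rule. That applies to PFS and TTP, and to best response in the association list. Progression status and axitinib duration come close: every refractory patient has progressed by definition, and time on drug largely follows time to progression.

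OS differs. It is not fixed by the grouping, but the two groups enter with unequal survival guarantees from axitinib start. A long responder has by definition lived 9 months. A refractory patient has by definition lived only to the documented PD. The gap favours long responders even if death rates are equal afterwards.

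An OS p-value, or an OS median by group without a caveat, could be taken to show that long response prolongs survival when part of the difference comes from selection. Neither the SAP nor Protocol 8.9 (limitations) warns of this.

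**Working it through.** The plan gives no power, event count or calculated sample size for this comparison, so there is no figure of its own to reproduce.

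**Inputs from the documents**
- About 60 patients (Protocol 8.5; SAP 2.1) at about 2:1 (Protocol abstract, study population), taken as 40 long responders and 20 refractory.
- Median OS of 13.6, 20.1 and 29.9 months, and median PFS of 6.7 and 4.8 months, for axitinib (Protocol 6.1.6).
- Median prior sunitinib duration of 9.7 months (Protocol 6.1.6), used as first-line duration.

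**Assumptions not in the documents:** exponential times; censoring uniform over 12 to 60 months from axitinib start; PD either uniform over 0 to 3 months or at exactly 3 months.

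**1. PFS and TTP.** Suppose all 20 refractory events come before month 9 and no long-responder event does. After the 20th event only long responders are at risk, so later times add nothing. Observed long-responder events over this span are 0, and chi-square = E²/V.
- Distinct event times: E = Σ 40/n for n = 41 to 60 = 16.05; V = Σ 40(n − 40)/n² = 2.995; chi-square = 16.05²/2.995 = 86.1, p about 1.7 × 10⁻²⁰.
- All tied at 3 months: E = 20 × 40/60 = 13.33; V = 20 × (40/60) × (20/60) × (40/59) = 3.013; chi-square = 59.0.

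Even 4 versus 2 patients, fully separated, gives p = 0.018.

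**2. Best response.** PD in 20/20 versus 0/40 has Fisher p = 1/C(60,20) = 2.4 × 10⁻¹⁶.

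**3. OS with equal death hazards.** OS = guaranteed time + exponential time with the same hazard in both groups. The guarantee is 9 months for long responders and time to PD for refractory patients. Rejection by the two-sided 5% log-rank test in 8,000 runs:

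| Outcome | PD timing | Median 13.6 | 20.1 | 29.9 |
|---|---|---|---|---|
| OS from axitinib | 0–3 months | 37.7% | 25.0% | 16.8% |
| OS from axitinib | 3 months | 29.1% | 19.0% | 13.9% |
| OS from first line | 0–3 months | 24.3% | 19.3% | 14.4% |
| OS from first line | 3 months | 19.4% | 15.0% | 12.0% |

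Control: with each patient's clock started when the guarantee ends, rejection is 4.8% to 5.5%.

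**4. Second construction.** One homogeneous population, with death independent of progression, is grouped as PFS of at least 9 months versus progression by month 3 (1,500 runs per scenario; first-line median set at 11 months). At 40 versus 20, PFS and TTP reject in 100% of runs, OS in 15.5% to 39.6% and OS from first line in 12.9% to 24.4%. OS restricted to patients alive and in follow-up at 9 months rejects in 4.6% to 6.2%.

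**5. Sample size.** In the step 3 model, OS rejection is 12.4% to 32.3% at 30 versus 15 and 17.4% to 48.6% at 60 versus 30.

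**The case against.** **No test is written down.** Efficacy is only to be analysed and compared, while the baseline sentence carries the word for statistical testing. The log-rank rule is conditional on need, and SAP 7.1, SAP 9.2 for secondary objectives and Protocol section 8 all point to description. This stands, so the point is conditional. A reader might infer that the SAP commits to a log-rank test of PFS between the groups; the text does not say so. It does leave the matter open, because the sentence sits under the primary objective, outside the descriptive rule for secondary objectives.

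**The by-group analyses in SAP 7.2 are already descriptive.** This also stands. A reader might count them all as further circular tests, but SAP 9.2 makes secondary objectives descriptive. The first by-line block in 7.2 reads more naturally as line 2 versus line 3 or later within each response group.

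**Separation is not absolute.** Correct: SAP 7 sets no PFS limit for refractory patients, so a late first assessment could weaken it. Near-certain is the right word.

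**Kaplan-Meier OS by group correctly describes the groups as defined.** True; it misleads only if read causally, and the SAP makes no such claim. That supports a footnote, not removal.

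**Other items measured after axitinib start.** A reader might extend the argument to suspension, further treatment, ECOG at the end of axitinib and IMDC group at discontinuation. None of these defines a group, and no bias has been shown for them. Vital status is barely affected (4.8% to 9.2% rejection in the step 3 model).

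**Conclusion.** The point holds in conditional form. SAP 9.2, read with SAP 9.1, invites between-group tests that would be uninformative for PFS and TTP and biased towards long responders for OS from axitinib start and, less strongly, for OS from first line. Best response, progression status and axitinib duration in the SAP 7.1 list raise the same difficulty as PFS.

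At 40 versus 20 with equal death hazards, an OS test would reject in about 14% to 40% of studies and a first-line OS test in about 12% to 24%, against a nominal 5%. These sizes rest on the assumed exponential times, censoring and group sizes, and on PD within 3 months; later PD would shrink them. Equal hazards is a device to isolate the guarantee, so the figures do not say how much of an actual OS gap would be artefact.

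A reader might conclude that the search for predictive factors is compromised. It is not: the logistic model admits only factors that precede axitinib. Severity is minor to should-fix.

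**What to change.** 1. In SAP 9.2, replace the efficacy sentence with: PFS, TTP, OS and OS from first line will be described by group (Kaplan-Meier median, 95% CI, events, censored) without between-group tests, because the groups are defined by PFS and best response.
2. In SAP 7.1, show best response, progression status and axitinib duration by group without p-values. Moving the other items measured after axitinib start is optional.
3. Footnote every by-group OS table and figure, including those under SAP 7.2: long responders survive at least 9 months by definition, so the difference between groups must not be read as an effect of response on survival.
4. Any OS comparison from a 9-month landmark is optional and labelled exploratory. It drops refractory patients who die before month 9, and the SAP should say so. No landmark rescues PFS or TTP.

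The cost is a few lines of SAP wording, one footnote and small changes to table shells, with no new data. Every estimate is kept; the p-values given up are uninformative or biased.

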### Secondary objectives

A descriptive analysis will be performed on all secondary objectives.

### Safety objectives

The number of patients with at least one AA, and the number of registered AAs will be analysed. The number of AAs per patient will be described

A descriptive analysis will be performed of the different adverse events reported during treatment with axitinib, their frequency, the worst grade according to CTCAE, the cycle in which the worst grade occurred, the relationship with the treatment, whether the AE was serious and, if so, the reason why it was considered serious.

section will be added indicating the number of patients with at least one AA related to the treatment, and the number of related AAs registered. The descriptive analysis of treatment-related AAs will be performed according to the worst grade according to CTCAE by patients.

A section will be added indicating the number of patients with at least one severe AA and the number of serious AAs registered. The descriptive analysis of the reason for the severity of AAs will be carried out and a list with the information of these serious AAs will be displayed (site, patient, AA, worse CTCAE grade, cycle in which it has been worse grade, relationship with treatment, reason for severity).

### Other analyses

A descriptive analysis will be performed of all variables that do not cover any of the above objectives, and which have been recorded in the CRF.

Observations to the descriptive analyzes:

- **SUBSEQUENT TREATMENTS:** The section on subsequent treatments will be analyzed in patients who have indicated suspension of axitinib treatment.

And in this set, the number of lines after axitinib registered will be obtained on the total number of patients and on patients with Have you received any subsequent treatment? = Yes. On this set of patients, post-axitinib treatments will also be analyzed as follows:

- **First post-axitinib treatment:** the drug received, and the best response achieved will be analyzed if the treatment continues. If it does not continue, the reason for the discontinuation will be analyzed (specifying if there are other reasons).

- **Second line and after suspension with axitinib:** a list with the registered data of these treatments will be shown.

- **DOSE MODIFICATION:** It will be described how many patients have modified doses and how many modifications have been registered. In patients with modification, the following elements will be described:

- **Type of modification** (the variables included in the CRD will be analyzed. This analysis should not be confused with the definition included in section 7 definition of variables and objectives of this document).

- **The changes registered** will be ordered in order of occurrence (1st modification, 2nd modification ... until the last one), and for each order the following will be described: the type of modification, the new dose and the reasons for modification.

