## 7.2. Secondary objectives:

- To describe the response to treatment with axitinib in the long-term responder group (defined as a PFS of at least 9 months with the drug)
- To describe the efficacy per treatment line (second line of treatment and subsequent)
  - Best response to treatment (CR, PR, SD)
  - Progression-free Survival
  - Objective response rate (ORR) and clinical benefit (sum of CR, PR and SD)
  - Time to progression
  - Overall Survival
- To describe the duration of treatment with axitinib
- To describe the percentage of patients who titrated doses of axitinib of more than 5 mg twice daily

- To describe the percentage of patients who have reduced doses of axitinib to below 5 mg twice daily
- To describe the tolerability of axitinib
- To describe the treatments received at progression
- To describe the response to the treatments received at progression

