## 8.10. Further aspects

### - Study procedures:

For the inclusion of patients in the study, the Investigator must review the inclusion/exclusion criteria and, in the case of including patients who are alive and being followed-up at the site, the patient will be required to sign the ICF before inclusion in the study, as per the model appended to the protocol.

For patients who have already died at the time of inclusion in the study, the request for informed consent is not required, as is permitted in order SAS/3470/2009 of 16 December, on observational post-authorisation studies.

With the data available in the medical record, the requested information will be recorded in the electronic case report form in order to analyse the study variables. Lists of these variables, such as Annex I, are attached to the protocol.

- Review and confirmation of meeting the inclusion criteria and not meeting the exclusion criteria for the study.

- In the case of living patients who are subject to follow-up at the site, the patient must receive an explanation of the procedures and purpose of the study, and be requested to sign the ICF if he/she wishes to participate in the study.

- Data on demographic characteristics

- Disease history:

- Patient's medical records
- Data on the disease for which he/she is receiving treatment with axitinib
- Data on previous treatments received for the disease.

- Data on the treatment with axitinib

- Information on the patient's response to the treatment

- Information on the tolerability and management of treatment with axitinib
- Information on survival and dates of progression (if any)
- Information on subsequent treatment(s) received (if any).
- Information on the patient's vital signs in the last follow-up performed.

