It will be calculated as follows: Progression Free Survival to sunitinib (SLP, in months) = (Date of Progression of the Disease to treatment with sunitinib - Start date of treatment with sunitinib) / 30,4375. If there is no progression, the case is censored in SLP (months) = (Start date of treatment with axitinib - Start date of treatment with sunitinib) / 30,4375.

- **Majority sequence**

The number of patients receiving the second-line treatment will be shown, following the sequence that is most observed in all the patients included (SUT-AXI-NIVO).

The following analyzes will be carried out by group (long responders / refractories):

- Best treatment response (CR, PR, SD, DP).
- Duration of treatment (months).
- Progression-free survival. PFS will be shown in all patients with sunitinib-axitinib sequence and PFS per group.
- Objective response rate (ORR) and clinical benefit.
- Time to Progression
- Overall Survival. OS will be shown in all patients with sunitinib-axitinib sequence and OS per group
- Overall Survival since the beginning of 1st line. OS will be shown in all patients with sunitinib-axitinib sequence and OS per group

It is defined as: Global Survival from the beginning of the first line (SG, in months) = (Exit date - Start date of first line treatment) / 30,4375. If there is no exitus the case is censored in Global Survival (SG, in months) = (Date of last control - Start date of the first treatment) / 30,4375.

- To describe the duration of treatment with axitinib. It will be described as it is described in section 7. Definition of variables and objectives
- To describe the percentage of patients who had increase the dose of axitinib above 5 mg twice daily. It will be described as it is described in section 7. Definition of variables and objectives
- To describe the percentage of patients who had reduce the dose of axitinib below 5 mg twice daily. It will be described as it is described in section 7. Definition of variables and objectives
- To describe the tolerability of axitinib (see point 9.2. Statistical analyses, Safety objectives).
- To describe the response to treatments received at progression. The treatments received will be described in cases of DP for first-line, 2nd line, etc.; that is, in treatments prior to axitinib.
- Overall survival based on post treatment
  - o Overall survival. The OS will be displayed according to having received further treatment (Yes vs. No).

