  - o The following analyzes will be carried out in the patient population depending on whether or not they have had subsequent treatment;
    - OS per group (LR vs RF).
    - OS per axitinib line (2 VS  $\geq 3$ ).
    - OS per group (LR vs RF) for patients with axitinib in line 2.
    - OS per group (LR vs RF) for patients with axitinib online  $\geq 3$ .
- Overall survival based on most recent subsequent treatment.

The following analyzes will be performed in this subpopulation of patients in the groups of patients who have had the 2 most common subsequent treatments:

- o OS
- o OS per group (LR vs RF)
- o OS per axitinib line
- o OS per group (LR vs RF) for patients with axitinib online 2
- o OS per group (LR vs RF) for patients with axitinib online  $\geq 3$
- To describe treatments received at progression. The treatments received in the cases of PD for first line, 2nd line etc ... it means, in the treatments previous to axitinib will be described. The analysis of post-axitinib treatments will be shown as explained in section 9.2 Statistical analysis.

The responses of the previous treatments to axitinib initiated by PD in the different registered lines will be presented.

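### As worded, SAP 9.2 analyses best response to the first post-axitinib treatment only while that treatment continues, and SAP 7.2 ties the matching objective to lines before axitinib

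*SAP*

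**What the plan says.** Protocol 7.2 lists items on axitinib response, treatment duration, dose changes and tolerability. It then gives two descriptive objectives on therapy at progression: which treatments were received, and "To describe the response to the treatments received at progression". Protocol 8.10 (Study procedures) collects subsequent treatments as an item separate from previous ones.

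SAP 7.2 makes the response objective operational as follows: "The treatments received will be described in cases of DP for first-line, 2nd line, etc.; that is, in treatments prior to axitinib". Under the companion objective on which treatments were received, it repeats the restriction to lines before axitinib and adds: "The responses of the previous treatments to axitinib initiated by PD in the different registered lines will be presented". It then refers the reader onward: "The analysis of post-axitinib treatments will be shown as explained in section 9.2 Statistical analysis".

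SAP 9.2 (Other analyses, Subsequent treatments) works in patients who stopped axitinib. For the first treatment after axitinib, "the drug received, and the best response achieved will be analyzed if the treatment continues". The next sentence reads: "If it does not continue, the reason for the discontinuation will be analyzed". For later lines, "a list with the registered data of these treatments will be shown".

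The CRF variables in SAP 6 hold, for a subsequent treatment, the drug, dates, an ongoing flag, the best response (with progression and not evaluable as categories) and the reason for discontinuation. These are separate fields; recording of best response does not depend on the treatment being ongoing.

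**The concern.** There are two linked problems of wording.

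First, the objective reads most naturally as what happens after axitinib fails, since it closes a list about axitinib and the protocol collects subsequent therapy for its own sake. SAP 7.2 attaches it to lines that ended before axitinib began. Post-axitinib response then depends wholly on SAP 9.2.

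Second, SAP 9.2 makes the best-response analysis conditional on the treatment still running. Still being on a drug is partly a consequence of responding to it, so a response rate in that group is selected on outcome. If the text is programmed as it stands, the report would give a response rate for post-axitinib therapy from a small group that does not represent those who received it. Nothing in the table would warn the reader.

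**Working it through.** The plan states no figure for this point, so there is nothing to reproduce. The check is a comparison of texts, followed by an illustration with assumed inputs.

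**Step 1. Does any other text restore an unconditional summary?**

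- SAP 9.2, Secondary objectives, promises a descriptive analysis of all of them, but SAP 7.2 has defined this one on pre-axitinib lines.
- The catch-all in SAP 9.2, Other analyses, covers CRF variables that serve none of the objectives. Best response to subsequent treatment does serve one.
- SAP 7.2 rules out PFS and time to progression for subsequent treatments because no progression date is collected. This hints that response was still intended, but the analyses listed there are by the line in which axitinib was given.
- The table list in SAP 10 gives best response its own entry for first-line, second-line, third-line and axitinib treatment. Subsequent treatments (table 7) has no sub-entries.

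None of these clearly supplies the missing analysis.

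**Step 2. Who is excluded under the literal rule?** Everyone whose first post-axitinib treatment has ended, whether through progression, toxicity, another reason or death. A patient who responded and later stopped loses the response. A patient with progression as best response who is still being treated stays in. Protocol 9.1 expects many patients to have died before inclusion, and Protocol 8.5 expects about 60 patients in all, so few may remain.

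**Step 3. How far could the rate move?** Let p be the true objective response rate among all who received a first post-axitinib treatment. Let f_R and f_N be the shares of responders and non-responders still on it. Then

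share analysed = p·f_R + (1 − p)·f_N

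rate among ongoing = p·f_R / [p·f_R + (1 − p)·f_N]

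All inputs are assumed. For p = 20%, f_R = 40% and f_N = 10%: 0.08 / (0.08 + 0.08) = 50%, with 16% of treated patients analysed. The range is:

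| f_R / f_N | p = 10% | p = 20% | p = 30% | Share analysed |
|---|---|---|---|---|
| 20% / 20% | 10% | 20% | 30% | 20% |
| 30% / 15% | 18% | 33% | 46% | 16.5–19.5% |
| 40% / 10% | 31% | 50% | 63% | 13–19% |
| 60% / 10% | 40% | 60% | 72% | 15–25% |

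Clinical benefit behaves in the same way. With a true rate of 60%, and 5% of patients with progression against 20% of the others still on treatment, the ongoing-only rate is 0.12 / (0.12 + 0.02) = 86%. With 0% against 20% it is 100%.

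**Step 4. Can treatment duration alone produce such selection?** Assume 25% response, 35% stable disease and 40% progression. Assume exponential durations with means d = 18, 8 and 2.5 months, and time since start uniform over T = 36 months. The share still on treatment is (d/T)(1 − e^(−T/d)), which gives 43%, 22% and 7%. Overall, 0.25 × 0.43 + 0.35 × 0.22 + 0.40 × 0.07 ≈ 21% are ongoing. Among them response is 51% (true 25%) and progression 13% (true 40%). This is one invented scenario and shows the mechanism only.

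**The case against.** The strongest reply is that the sentence is a translation slip. It follows the CRF fields: drug, ongoing, best response, reason for discontinuation. The likely intent is drug, best response and *whether* treatment continues, with the reason if it does not. The condition, read literally, could also govern the drug received. Yet SAP 7.2 forms survival groups from the two most common subsequent treatments, which requires the drug for everyone. SAP 7 computes the duration of all subsequent treatments, stopped or ongoing. Untranslated Spanish abbreviations elsewhere in the SAP make a slip plausible. This stands as the probable explanation, but it does not remove the point: the sentence that follows turns the condition into an either/or, and a programmer following the text would restrict the response table.

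A second reply is that SAP 7.2 does not ignore post-axitinib treatments, because it points to SAP 9.2, and that the protocol says at progression, not after axitinib. Both are true. A reader might infer that post-axitinib therapy is left out of the plan; the pointer shows that it is not. The post-axitinib reading of the objective is an inference from its context in Protocol 7.2 and from the separate data item in Protocol 8.10.

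A reader might also object that SAP 9.2 takes all patients who stopped axitinib, not only those who stopped for progression. That is minor: the set is stated openly, and the CRF holds the reason for stopping, so the subset can be formed.

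**Conclusion.** The point holds as a defect of wording that would bias one descriptive secondary result if followed literally. SAP 7.2 places the objective on pre-axitinib lines, and the only operative text on response after axitinib conditions it on continuation.

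The direction is upward whenever responders are more likely than non-responders to be still on treatment. If continuation is unrelated to response there is no bias. The size is unknown; the range of 20% to 60% for a true rate of 20% rests entirely on assumed continuation shares.

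Three stronger readings go beyond the documents:

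- That the rule drops the patients who progressed. It drops everyone who stopped, for any reason, and keeps a patient treated beyond progression.
- That the ongoing group would be mostly responders. Even in the duration scenario above, 49% are not, and the documents give no figure.
- That the sponsor chose a biased analysis. The surrounding text points to unclear drafting.

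The comparison of long-term responders with refractory patients does not use this variable and is not affected.

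**What to change.** In SAP 9.2, state that the drug and best response to the first post-axitinib treatment are tabulated for all patients who received one, with not evaluable and missing shown as categories. Report continuation status and, for those who stopped, the reason for stopping as separate items.

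In SAP 7.2, define both at-progression objectives on treatments started after axitinib. Optionally add the subset who stopped axitinib for progression. Describe the pre-axitinib lines under their own heading.

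The cost is a few sentences in the SAP and, if the literal rule was programmed, one table to rerun. Every field needed is already in the CRF. The SAP's amendment table says version 3 followed a review of draft results, so the sponsor can check how the draft table was built.
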